### **6.5.2. Lost to Follow-Up**

Lost to follow-up is defined by the inability to reach the subject by the end of the study, only. No subject should be considered lost to follow-up, until the study has been completed. If a subject does not return for a scheduled visit, every effort should be made to contact the subject. Attempts to reschedule the visit should be completed by phone, e-mail, text message, and if necessary, by letter and/or certified mail, in instances where the subject is not responsive to contact attempts. This includes follow-up with persons authorized by the subject as noted above. The study retention team must be contacted, through the retention hotline or delegate, to discuss strategies available for assistance with locating subjects who are potentially lost to follow-up. All efforts to retain a subject, should continue throughout the course of the study and should be documented in the subject's medical source records. Every effort should be made to have the subject complete an EDC or EOS visit and to document subject's vital status, if possible.

If it is determined that the subject has died, the site will use permissible local methods to obtain the date and cause of death. If investigator's use of third-party representative to assist in the follow-up portion of the study has been included in the subject's informed consent, then the investigator may use a Sponsor retained third-party representative to assist site staff with obtaining subject's contact information or other public vital status data necessary to complete the follow-up portion of the study. The site staff and representative will consult publicly available sources, such as public health registries and databases, in order to obtain updated contact information. If after all attempts, the subject remains lost to follow-up, then the last known alive date as determined by the investigator should be reported and documented in the subject's medical records.

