The trial is intended to complete when approximately 844 subjects have accrued adjudicated and confirmed primary endpoint events, or 12 months following the randomization date of the last subject, whichever occurs later.

The sample size may be modified to shorten the expected duration of the trial or to improve the likelihood of attaining 70% power, for the key secondary composite endpoint of CV death, non-fatal MI and non-fatal stroke. Prior to the end of enrollment, blinded assessments will be made of the expected duration of the trial and of the power for this endpoint, assuming a hazard ratio (HR) of 0.8 at a two-sided alpha of 0.05. The decision to make either or both modifications will be documented in the Trial Master File. If the modification for the key secondary endpoint is made, the trial would be intended to complete when approximately 844 subjects have accrued adjudicated and confirmed primary endpoint events, 496 subjects have accrued adjudicated and confirmed events of the above key secondary endpoint, or 12 months following the randomization date of the last subject, whichever is last.

In addition, the sample size in certain subgroups, including diabetic subjects with no prior CVD event, may be modified or the trial duration may be extended to improve the likelihood that the estimated hazard ratios in the subgroups are less than one. Prior to the end of enrollment, the sponsor will perform a blinded assessment of the probabilities, assuming a hazard ratio of 0.8. If one or more of the probabilities are too small, the number of subjects in the corresponding subgroups may be modified, possibly increasing the total enrollment to do so. Prior to the end of the study, the sponsor will perform a second blinded assessment of the probabilities. If one or more of these probabilities are too small, the duration of the trial may be extended. If the latter modification is made, the criterion for stopping the trial will include accruing 58 primary endpoint events in the corresponding subgroups. These decisions will be documented in the Trial Master File.

Randomized subjects who withdraw from the study will have consented, at the onset of the study, to provide vital status information to the study site at the completion of the study.

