5. ANALYSIS SETS

5.1. Full Analysis Set

The Full Analysis Set (FAS) includes all subjects who were randomized, excluding fraudulent subjects who attempted to be randomized more than once into a bococizumab cardiovascular outcomes trial (B1481022 or B1481038). Subjects will be analyzed according to their randomized dose regardless of any change in dose. Data will not be excluded from the FAS due to changes in dose or adherence to, or discontinuation of, study medication. With the discontinuation of the bococizumab development program, the efficacy cutoff date will not be used. All data will be included.

5.2. 'Per Protocol' Analysis Set

Not applicable.

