7. HANDLING OF MISSING VALUES

For the clinical endpoints, not all subjects will have adjudicated and confirmed events. Subjects who do not experience any of the components of the primary endpoint will be censored on the date of last contact or 01November2016, whichever comes first. The date of last contact is defined as the date of death, if the date is not missing. Otherwise, the date of

last contact is defined as the study discontinuation date, the date of last visit, the date of last telephone contact, the onset date of the last AE, or the randomization date, whichever occurs last. The same censoring will be done for all other clinical endpoints and time to discontinuation from study. For analyses in the SAS, the date of first dose will be substituted for the randomization date.

Missing values for the Digit Span Forward, Digit Span Backward, Digit Symbol - Coding, Trail Making A and Trail Making B tests and the HVLT will not be imputed. For the Digit Span Forward and the Digit Span Backward, if the maximum number of digits is not reached and the last result is not a zero, the value will be missing.

Missing values for the PHQ-2 and PHQ-9 will not be imputed. If at least one item is missing, the total scores will be missing.

For all other efficacy and safety endpoints, missing values will not be imputed; missing values will remain missing.

For longitudinal analyses of circulating biomarker endpoints, a mixed model repeated measures (MMRM) model will be used for the analyses. As a likelihood method, MMRM models are valid when the data are missing at random (MAR). All subjects with a non-missing baseline value and at least one non-missing post-baseline value will be included in these analyses. Subjects with a missing baseline value will not contribute to the analyses. Consistent with MMRM model fitting, no explicit imputation of missing assessments will be performed.

Percent changes from baseline to last post-baseline value in LDL-C will be analyzed by analysis of covariance (ANCOVA). As a likelihood method, ANCOVA is valid when the data are MAR. Subjects with a non-missing baseline value and at least one non-missing post-baseline value will be included in the analyses. Subjects with a missing baseline value or without a non-missing post-baseline value will not contribute to the analyses.

When forming subgroups, subjects with a missing value on the classifying variable will not be included in a subgroup.

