If an imputed time to event would put the event date after 01November2016, the event will be censored and the imputed event time will be truncated so that the time to event is on 01November2016.

The completed data sets will be analyzed with the Cox proportional hazards model used for the primary analysis. This will be repeated for 100 data sets and the estimates of the log hazard ratio and their standard errors will be combined to form point estimates and confidence intervals using standard multiple imputation methodology (Rubin, 1987). The MI-based estimates and their confidence intervals will then be back-transformed to the hazard ratio scale. The estimated hazard ratio and a 95% confidence interval will be reported.

The reasons for censoring for the primary endpoint will be summarized by treatment group.

Supplemental analyses

Investigator-reported potential primary endpoint events will be listed.

The number and percent of each component of the primary endpoint that occurs first will be summarized by treatment group.

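### For all-cause death, the SAP carries a withdrawn subject forward if records show a death, but not if records show the subject alive

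*SAP*

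**What the plan says.** **Censoring rule.** SAP section 7, repeated in 8.2.1, censors event-free subjects at the earlier of last contact and 01 November 2016. On last contact it says: "The date of last contact is defined as the date of death, if the date is not missing". Failing that, it is the latest of study discontinuation, last visit, "the date of last telephone contact, the onset date of the last AE, or the randomization date, whichever occurs last".

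**Scope.** SAP section 7 adds: "The same censoring will be done for all other clinical endpoints and time to discontinuation from study". All-cause death is therefore covered, as are the composites that contain death.

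**Data retained.** SAP 5.1 says of the Full Analysis Set: "All data will be included". Neither document excludes deaths found after study discontinuation.

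**Vital status.** SAP 2.1: "Randomized subjects who withdraw from the study will have consented, at the onset of the study, to provide vital status information". Protocol section 7 requires vital status for each randomized subject at study completion. Protocol 6.5.1 allows public sources where local law permits. For a subject who stays lost after all attempts, Protocol 6.5.2 says that "the last known alive date as determined by the investigator should be reported". The SAP's list of contact dates does not include that date.

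**Assumption and safeguard.** SAP 8.1.1.1 states that the log rank, Cox and Kaplan-Meier methods need censoring to be independent of the hazard. The multiple imputation for informative censoring in SAP 8.2.1 is limited to the primary endpoint.

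**The concern.** Suppose two subjects withdraw on the same day and a later records search finds one dead and the other alive. The first contributes an event and all the time up to death. The second is censored back at withdrawal, or at the last visit, call or adverse event if later, although the same search shows survival beyond that date. Time after withdrawal then enters the denominator only for those who died.

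Two results are at stake. Death rates per 100 subject-years, which SAP 8.1.1.1 reports with confidence intervals, come out too high in both arms. If the arms withdraw at different rates, the inflation differs and the hazard ratio for death moves against the arm that withdraws more.

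**Working it through.** **The plan's own figure.** The documents give no figure for this effect. The design figures do reproduce: 4(1.960 + 1.282)²/(ln 0.8)² = 844 events for 90% power at two-sided 0.05.

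**Inputs from Protocol 9.1.** Premature discontinuation 1% per year; 8,500 per arm; recruitment over 3.1 years with half the subjects in the last ten months; total duration 4.8 years.

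**Assumptions.** All-cause death at 0.5% to 3% per year (not given in the documents); uniform accrual within each half; constant hazards; every death after withdrawal is found by the cutoff; every living withdrawn subject is censored at withdrawal. The last two make the results upper bounds.

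**Formula.** Let T be potential follow-up, m the death rate and w the withdrawal rate. Deaths counted are about m·E[T]. Time lost by censoring living withdrawn subjects early is about w·E[T²]/2. The relative inflation of the death rate is therefore about w·k, with k = E[T²]/(2E[T]). To first order m cancels.

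**Death-rate inflation at w = 1% per year**
- Planned 4.8 years: half the subjects have T uniform on 2.533 to 4.8, half on 1.7 to 2.533. E[T] = 2.892, E[T²] = 9.205, k = 9.205/5.783 = 1.592. Inflation is 1.6%. Numerical integration gives 1.5% to 1.6% across the death rates; at m = 1% the rate reads 1.016 instead of 1.000 per 100 subject-years.
- Follow-up uniform on 0.2 to 3.0 years (an assumed shorter trial): E[T] = 1.6, E[T²] = 3.213, k = 1.004. Inflation is 1.0%.
- Cutoff at 3.1 years (an assumed early stop): E[T] = 1.192, E[T²] = 2.264, k = 0.950. Inflation is about 0.9%.

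**Hazard ratio when the true value is 1.** This is about (1 + w₁k)/(1 + w₀k). At 1% versus 2% over 4.8 years: 1.0318/1.0159 = 1.016. Numerical integration at m = 1% gives:

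| Withdrawal per year | 4.8 years | 4.8 years, half of later deaths found | 3.1 years |
|---|---|---|---|
| 1% v 1% | 1.000 | 1.000 | 1.000 |
| 1% v 1.5% | 1.008 | 1.004 | 1.005 |
| 1% v 2% | 1.016 | 1.008 | 1.009 |
| 1% v 3% | 1.031 | 1.016 | 1.019 |
| 2% v 5% | 1.047 | 1.024 | 1.028 |

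At m = 2% each entry changes by 0.001 or less.

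**Simulated log rank test** (8,500 per arm, 4.8 years, m = 1% or 2%, 1,500 replicates, Monte Carlo error about 0.6 points). Under the SAP rule two-sided type I error is 4.9% to 5.7% at 1% versus 2%, and 6.4% to 7.6% at 1% versus 3%. In the latter case 5.6% to 6.5% lies in the tail for harm to the arm that withdraws more, against 2.5% nominal. If living subjects are carried to the vital-status date, or deaths after withdrawal are not counted, the hazard ratio is 0.998 to 1.004 and the error 4.3% to 5.5% in every scenario, including equal withdrawal.

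No figure was computed for the composites.

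**The case against.** The strongest reply is that the gap is narrow and its effect is lost in sampling error. Several parts of that stand.

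- A reader might infer that no withdrawn subject found alive is carried forward. The text does not support this. Last visit and last telephone contact are on the list, so a subject confirmed alive by either is followed to that date. Only status learned solely from records, registries or third parties is missed.
- A reader might also infer that observed events have no upper date, since SAP 5.1 says "the efficacy cutoff date will not be used. All data will be included" while for imputed events 8.2.1 says "If an imputed time to event would put the event date after 01November2016, the event will be censored". But SAP 6.1 records that sites were told to forward for adjudication only events up to 01 November 2016, and endpoints must be adjudicated and confirmed. The cap already applies in practice.
- Lost subjects are mostly unaffected. Under Protocol 6.5.2 nobody is lost until the study is completed, so their discontinuation date may fall at study end. Under Protocol 6.5.1, withdrawing consent for disclosure stops data collection, so neither outcome should count.
- For the primary endpoint, the imputation fills in time for surviving subjects who left early. Discontinuation is also compared by arm, so an imbalance would be visible.
- All-cause death is outside the fixed testing sequence. With the 50 to 400 deaths tabulated in SAP section 3, the standard error of the log hazard ratio, 2/√d, is 0.28 to 0.10. A bias of ln 1.015 = 0.015 is 0.05 to 0.15 of that.

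These points limit the size but do not remove the asymmetry. The imputation does not extend to all-cause death or to the key secondary composites, and comparing discontinuation by arm shows an imbalance without correcting for it.

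**Conclusion.** The point holds for all-cause death, for withdrawn subjects whose vital status comes only from records or third parties. For them the censoring date depends on the outcome, contrary to the SAP's own stated assumption, and no sensitivity analysis addresses it.

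The size is small: about 1.0% to 1.6% on the death rate at 1% per year discontinuation, no bias in the hazard ratio if the arms withdraw equally, about 1.015 at 1% versus 2% and 1.03 at 1% versus 3%. The unequal rates are illustrations; the documents give only the 1%. The figures assume that all later deaths are found and that no living withdrawn subject is reached by visit or call; finding half the deaths roughly halves the bias.

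A reader might go on to infer that the primary result is at risk. The documents do not support that. The primary endpoint and the first three key secondary composites contain death and share the asymmetry, but the primary has its imputation. There is also an opposing effect: a withdrawn subject who later dies of a non-cardiovascular cause stays event-free for the primary endpoint until death, adding time in which non-fatal events may have gone unobserved. The net effect on the composites was not sized.

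**What to change.** 1. For all-cause death, add the date last known alive, from any source, to the dates that define last contact in SAP 7 and 8.2.1, capped at 01 November 2016.
2. For composites with non-fatal components, do not carry living withdrawn subjects to the vital-status date, because non-fatal events were not ascertained in that time. Add a sensitivity analysis that ends follow-up at study discontinuation for all withdrawn subjects and does not count later deaths. Keeping adjudicated deaths after withdrawal would leave the asymmetry in place.
3. No separate rule is needed for the 01 November 2016 event cap.

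This is a cheap improvement: a few SAP sentences, one derived date and one extra sensitivity analysis. The condition is that the date must be in the database. Protocol 6.5.2 asks for it to be reported and kept in the medical records, only for subjects who stay lost, and does not say that it is on the case report form. The sponsor should confirm this before unblinding.

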8. STATISTICAL METHODOLOGY AND STATISTICAL ANALYSES

8.1. Statistical Methods

8.1.1. Analyses for Continuous Data

8.1.1.1. Time-to-Event Endpoints

Time-to-event endpoints will be summarized by treatment group with the number of subjects at risk, the number and percentage of subjects with events, and event rates with 95% confidence intervals. Event rates will be calculated as the number of events per 100 subject-years at risk. The 95% confidence intervals will be calculated using an exact Clopper-Pearson method for Poisson random variables.

For the primary endpoint and the key secondary composite endpoint of cardiovascular death, non-fatal MI and non-fatal stroke, the number and percent of each component that occurs first will be summarized by treatment group. Events which occur on the day of, or the day after, the earliest event will be considered, and the following hierarchy will be applied:

1. CV Death,
2. Non-fatal MI,
3. Non-fatal stroke,
4. Hospitalization for unstable angina (if applicable).

For the primary endpoint and the key secondary composite endpoint of cardiovascular death, non-fatal MI and non-fatal stroke, the reasons for censoring will be summarized by treatment group.

Log rank test

Time-to-event endpoints will be tested with a log rank test stratified by geographic region and LDL-C at the pre-screening visit (<100 mg/dL, ≥ 100 mg/dL), and the two sided p-value from the stratified log rank test will be reported.

The log rank test is a non-parametric test of the equality of two distributions that allows for stratification and incorporates information about censoring. Stratification permits different event rates in different strata. The log rank test assumes that the censoring function is independent of the hazard function.

Cox proportional hazards regression

A Cox proportional hazards regression model for each endpoint other than time to discontinuation from therapy will be fit in the FAS with treatment group as a covariate and geographic region and LDL-C at the pre-screening visit (<100 mg/dL, ≥ 100 mg/dL) as stratification factors. For time to all-cause death and time to discontinuation from study therapy, the Cox proportional hazards model will be fit in the SAS with the same covariate and stratification factors. If the model fitting fails to converge, LDL-C at pre-screening will be removed as a stratification factor. The hazard ratios with corresponding 95% confidence intervals will be reported.

Cox proportional hazards regression is a semiparametric method for comparing hazard functions under the assumption of proportional hazards. The methodology can include adjustments for covariates for important prognostic factors, produces a point and interval estimate of the treatment effect, and allows for different baseline hazard functions in different strata to reflect different event rates in different strata. The methodology assumes that the censoring function is independent of the hazard function.

The goodness of fit of the Cox proportional hazards regression models for the primary endpoint and key secondary composite endpoint of cardiovascular death, non-fatal MI or non-fatal stroke will be assessed by plots of the cumulative expected number of events (estimated cumulative hazard rates) versus the observed cumulative number of events for each treatment arm within each stratum formed by the combination of the two stratification factors, using the method proposed by Arjas (1988). Departures from straight lines indicate a departure from proportional hazards, which may or may not affect the interpretability of the treatment effect.

Kaplan-Meier estimates

Kaplan-Meier estimates of time to first event will be plotted for the primary endpoint, the key composite secondary endpoint of cardiovascular death, non-fatal MI and non-fatal stroke, and for all-cause death.

Kaplan-Meier estimates are non-parametric estimates of the distribution of time to first event that incorporates information about censoring. The methodology assumes that the censoring function is independent of the hazard function.

Multiple imputations for Cox proportional hazards regression

The impact of informative censoring on the primary analysis will be evaluated through multiple imputations. Imputation will only be done for surviving subjects who discontinued from the study prematurely and did not have a primary endpoint event. Several imputation models for informative censoring will be used. The Weibull distribution will be used to generate the imputed values.

Multiple imputation is a flexible technique for incorporating the uncertainty in missing data that is ignored by single imputation methods, such as LOCF or worse case imputation. The imputation model need not be identical to the analysis model, which enables the exploration for different departures from MAR. It permits the use of standard software to be used to analyze each imputed data set under intention to treat. The results of the individual analyses are then combined into a single result using standard techniques (Rubin, 1987).

The Weibull distribution with shape parameter λ and scale parameter θ has a hazard function of the form $\lambda t^{\lambda-1}/\theta^\lambda$, which can accommodate both increasing and decreasing hazard functions.

8.1.1.2. Other Continuous Endpoints

Other continuous endpoints will be summarized by visit and treatment group using descriptive statistics, including the mean, standard deviation, median, first and third quartiles (Q1 and Q3, respectively), and minimum and maximum.

Mixed model for repeated measures

Percent changes from baseline in all lipid endpoints and hs-CRP and nominal changes from baseline in LDL-C will be analyzed using a mixed model repeated measures (MMRM) model with fixed effects for treatment (categorical variable), scheduled visit time point (categorical variable), baseline value (continuous variable), interaction between baseline value and scheduled visit time point, interaction between treatment and scheduled visit time point, and geographic region (categorical variable) and LDL-C at the pre-screening visit (<100 mg/dL, ≥100 mg/dL).

Restricted Maximum Likelihood (REML) estimation will be used, and the default covariance structure will be unstructured. Due to the slow onset of accrual in this event-driven trial, there will be few observations at the last several time points. One or more of the last visits may be removed to ensure convergence of the model fitting. Also, the geographic region with the fewest observations may be combined with the next smallest region to ensure convergence of the model fitting. This may be done twice. If the model fails to converge with an unstructured covariance matrix, a spatial power covariance will be used. If the model fails to converge with this covariance structure, compound symmetry will be used. Kenward-Roger degrees of freedom will be used. Estimates of treatment group means and mean treatment group differences using observed margins at Week 14 and each other visit, corresponding 95% confidence intervals, and p-value for the mean differences will be provided. The least-squares mean treatment group estimates and 95% confidence intervals will be plotted longitudinally.

For observed values of selected highly skewed circulating biomarker endpoints that are measured at more than one post-randomization visit, the same model will be fit in the same manner for log-transformed data. The data will be log transformed prior to calculating changes. Any zero values will be replaced with 0.0001 to enable taking the logarithm. The estimated treatment group means using observed margins and corresponding 95% confidence intervals from the analysis of the log-transformed data will be transformed to percent changes for reporting. The estimated treatment group differences will be transformed to the ratio of the mean percent changes and reported with transformed 95% confidence intervals along with untransformed p-values. The transformed estimated mean percent changes and corresponding transformed 95% confidence intervals will be plotted.

Changes from baseline in cognitive test results, including the Digit Span Forward score, Digit Span Backward Score, Digit Symbol - Coding score, Trail Making A score, Trail Making B score, HVLT Total Recall score, HVLT Delayed Recall Trial score, and the HVLT Recognition score will be analyzed using an MMRM model with fixed effects for treatment (categorical variable), scheduled visit time point (categorical variable), baseline value (continuous variable), interaction between baseline value and scheduled visit time point, and interaction between treatment and scheduled visit time point.

MMRM incorporates information from multiple visits and allows for covariate adjustment of the treatment effect so as to take important prognostic factors into account. Both of these increase the precision of the estimates and the power of the tests.

MMRM is a recommended approach for confirmatory trials (Mallinckrodt et al., 2008). The MMRM analysis is unbiased under the assumption that all missing data are either missing completely at random (MCAR) or missing at random (MAR) and is often robust to departures from MAR. Siddiqui, Hung, and O'Neill (2009) have shown that under various null and alternative hypotheses, the MMRM analysis estimates the true treatment group difference at the study endpoint with negligible bias even in the presence of a 1:1:1 mixture of MCAR, MAR, and missing not at random (MNAR) missing data mechanisms.

Analysis of Covariance

Continuous measurements assessed at a single post-randomization time point (i.e. the percent changes from baseline to last non-missing post-baseline measurement in LDL-C) will be analyzed using an analysis of covariance model with treatment group and baseline value as covariates and geographic region and LDL-C at the pre-screening visit (<100 mg/dL, ≥100 mg/dL) as factors. Kenward-Roger degrees of freedom will be used. Least squares means with corresponding 95% confidence intervals, the least-squares mean differences and corresponding 95% confidence intervals, and p-values will be presented.

ANCOVA allows for covariate adjustment of the treatment effect, increasing the precision of the estimates and the power of the tests. As a likelihood method, ANCOVA provides unbiased estimates under the MAR assumption.

